**REPORT OF PRIOR INVESTIGATIONS**

We seek permission to use the **Cordis Precise Pro Rx Nitinol Stent System** to treat intracranial dural venous sinus stenosis in patients with severe venous pulsatile tinnitus and severe lateral venous sinus stenosis.

The sponsor of this application has performed prior use of the device to treat symptomatic stenosis of dural venous sinuses in a series of more than 20 patients in the United States. Specifically, we have IDE approval to use this same device in a prospective clinical trial titled “Venous sinus stenting for Idiopathic Intracranial Hypertension refractory to medical therapy” (IDE# G090050), and 10 patients have been enrolled in this trial (last annual report attached). The anatomic location and the procedure of stent placement are identical in this protocol and IDE# G090050. Moreover, 10 additional patients with symptomatic venous sinus stenosis were treated outside the trial. There were no significant neurological or device related complications. Recently, a paper was published (Baomin et al. 2014) reporting on the results of 46 cases of pulsatile tinnitus and lateral (transverse and sigmoid) venous sinus stenosis treated with stenting using the Cordis Precise Pro Rx Nitinol Stent System. The procedure was successful in all 46 patients, resulting in resolution of tinnitus in all patients. There were no neurological or device related complications. Therefore, there are at least 66 cases of the Cordis Precise Pro Rx Nitinol Stent System used to treat stenosis of the lateral (transverse and sigmoid) venous sinus without severe procedural or neurological adverse events.

The Cordis Precise Pro Rx Nitinol Stent System Cordis is approved by the FDA under Premarket Approval (PMA) for carotid revascularization in patients at high-risk for adverse events from carotid endarterectomy and:

1.  $\geq 50\%$  common or internal carotid artery stenosis with associated neurological symptoms, or  $\geq 80\%$  common or internal carotid artery stenosis without associated neurological symptoms, and
2. Vessel diameter 4-9 mm at the target lesion.

## **INVESTIGATIONAL PLAN**

### **HYPOTHESIS AND OBJECTIVES**

Papers published during the last seven years show that in patients with venous pulsatile tinnitus and significant venous sinus stenosis, tinnitus improves or resolves after stenting in the vast majority of patients. There have been 100 patients with venous sinus stenosis and venous pulsatile tinnitus reported in the literature (Table 1, attached document).

Fifty-four of these patients had Idiopathic Intracranial Hypertension and venous pulsatile tinnitus and the rest had isolated venous pulsatile tinnitus. After stenting, the venous pulsatile tinnitus resolved in 93/100, improved in 4/100 and remained unchanged in 3/100. This corroborates our experience at Cornell; out of 18 patients with venous sinus stenosis and venous pulsatile tinnitus treated by the PI with stenting, 17 had immediate resolution of the tinnitus. In one patient the tinnitus remained unchanged (anecdotal evidence; paper submitted for publication).

Our hypothesis is that venous pulsatile tinnitus is caused by the venous sinus stenosis and stenting would offer effective and long-term resolution of these symptoms. Our project aims to evaluate the long-term efficacy of venous sinus stenting in patients with severe intractable venous pulsatile tinnitus.

#### **Primary Outcome:**

- The primary outcome will be complete or near-complete resolution of tinnitus at 12 months in more than 75% of treated patients.
- Primary Outcome Measure: No, slight, mild, or moderate tinnitus (grades 1, 2, and 3) on Tinnitus Handicap Inventory at 1, 6, 12, and 24 months

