## **Our experience treating patients with Idiopathic Intracranial Hypertension and pulsatile tinnitus using venous sinus stenting**

Our institution has had success treating patients (N=20) who have idiopathic intracranial hypertension (IIH) concomitant with pulsatile tinnitus (N=18). In addition to pulsatile tinnitus, IIH patients have symptoms of headache, diplopia, visual field deficits, hearing loss, and vertigo. These patients typically undergo a regimen of medication as the first line of treatment. If the IIH becomes refractory to maximal medication, surgery (shunt placement) or stenting are options for treatment. Stenting of the dural venous sinus has been shown to eliminate tinnitus among pseudotumor cerebri patients (Mathis et al. 1997), and we were able to replicate this effect in our study. We enrolled patients in the FDA approved trial “Venous sinus stenting in patients with idiopathic intracranial hypertension refractory to medical therapy” over a three-year period from January 2012-December 2014. Patients eligible for venous stenting outside the trial were enrolled in a prospective database. Out of the 20 patients, 18 experienced pulsatile tinnitus. Nine patients presented with grade-4, 5 patients had grade-3, and 2 patients each had grade-2 and grade-1 tinnitus. Out of eighteen patients with IIH and pulsatile tinnitus treated with venous sinus stenting, there was immediate resolution of tinnitus in seventeen patients. All patients had unilateral distal transverse-sigmoid sinus stenting. There was no recurrence of tinnitus for the duration of follow-up period. The 1 patient who had persistent tinnitus after the procedure had grade-1 tinnitus and did not report any change in severity. No serious neurological adverse events occurred after the procedure. All non-serious adverse events were treated without the need for invasive treatment. Of these, seven patients experienced headaches afterwards and were treated with steroids, one patient developed a small retroperitoneal hematoma, and another patient developed free intra-abdominal hemorrhagic fluid collection a few days after the procedure that was attributed to a ruptured hemorrhagic ovarian cyst. There were no neurological adverse events or device related complications.

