### **Inclusion and Exclusion Criteria**

#### Inclusion criteria:

- Severe or catastrophic venous pulsatile tinnitus defined as Grades 4 or 5 on Tinnitus Handicap Inventory
- 50% or more stenosis of the lateral venous sinus on MRV or CTV, ipsilateral to the side of more severe tinnitus
- Length of stenosis  $\leq$  70mm
- Transstenotic gradient  $\geq$  4mm Hg evidenced by venous manometry
- Failure of conservative or non-surgical therapies (including sound therapy, sound masking, hearing aids, tinnitus retraining (desensitization) therapy. Failure is

defined as Grades 4 or 5 on the Tinnitus Handicap Inventory despite prior treatments that have lasted for at least 3 months.

- Adults, age > 18 years
- Informed consent signed by the patient

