### **Endpoints**

#### Primary Endpoints:

- Safety Endpoint: absence of procedure related and device related complications.
- Efficacy Endpoint:
  - o Improvement of more than one grade in the Tinnitus Handicap Inventory Questionnaire at 1, 6, 12, and 24 months after stent placement.

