### **Number of Patients**

We wish for permission to enroll 20 patients in this study, all at New York Presbyterian/Weill Cornell Medical Center.

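### The protocol gives two different, unranked primary efficacy criteria, and one of them counts moderate tinnitus as complete or nearly complete resolution

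*Protocol*

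**What the plan says.** Two sections of the protocol define the primary efficacy result.

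- **Hypothesis and Objectives, Primary Outcome.** The outcome is "complete or near-complete resolution of tinnitus at 12 months in more than 75% of treated patients". The measure given for it is "No, slight, mild, or moderate tinnitus (grades 1, 2, and 3) on Tinnitus Handicap Inventory at 1, 6, 12, and 24 months". This is an absolute threshold: grade 3 or better.
- **Endpoints, Primary Endpoints.** The efficacy endpoint is "Improvement of more than one grade in the Tinnitus Handicap Inventory Questionnaire at 1, 6, 12, and 24 months after stent placement". This is a change from baseline: a fall of at least two grades. It carries no target proportion and no decisive visit.

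Three other places bear on the point. The inclusion criteria admit only "Severe or catastrophic venous pulsatile tinnitus defined as Grades 4 or 5 on Tinnitus Handicap Inventory". The Number of Patients section asks to "enroll 20 patients in this study". The Data Analysis section says only that a proportion will be reported for each endpoint; it does not say which criterion is the primary one.

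**The concern.** There are two separate faults.

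1. **Two primary criteria.** Both sections use the word primary, yet one is a threshold with a target and the other a change score without one. In a single-arm trial the central efficacy claim is one proportion, so its definition has to be fixed before the data are seen. As written, either proportion could be presented as the main result.
2. **A label that does not fit its measure.** The Primary Outcome section describes success as resolution that is complete or close to it, then counts moderate tinnitus as success. Since every patient starts at grade 4 or 5, anyone who falls below the entry threshold is reported as resolved or nearly so. The rationale for the trial uses the word more strictly. The literature summary separates resolved from improved patients: "resolved in 93/100, improved in 4/100 and remained unchanged in 3/100". In the sponsor's own series a patient left at grade 1 is called persistent: "The 1 patient who had persistent tinnitus after the procedure had grade-1 tinnitus and did not report any change in severity". Grade 1 would be a success under the Primary Outcome measure.

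At stake is what the trial's headline success rate means, and whether it was fixed in advance.

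**Working it through.** The protocol states no power or error-rate figure for this endpoint, so there is none to reproduce. The check has three steps.

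**Step 1: where the criteria disagree.** Inputs: baseline grade 4 or 5 (inclusion criteria); follow-up grade 0 to 5 (case report form). Criterion A is follow-up grade ≤ 3 (Primary Outcome). Criterion B is baseline minus follow-up ≥ 2 (Primary Endpoints).

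| Baseline | Follow-up | A | B |
|---|---|---|---|
| 4 | 0, 1, 2 | success | success |
| 4 | 3 | success | **failure** |
| 4 | 4, 5 | failure | failure |
| 5 | 0, 1, 2, 3 | success | success |
| 5 | 4, 5 | failure | failure |

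They differ in 1 of 12 cells, 4 to 3. B is nested in A, because every B success is an A success.

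**Step 2: size of the difference.** With 20 patients, each 4-to-3 patient moves the proportion by 1/20 = 5 points. More than 75% of 20 needs at least 16, since 15/20 is exactly 75%. For example, 19 of 20 at grade 3 or better is 95% under A. If 4 of those 19 went from 4 to 3, B gives 15/20 = 75%, which does not exceed the bar.

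The protocol attaches the 75% bar only to A; applying it to B is an assumption for illustration. Let a be the probability of meeting both criteria, b of going from 4 to 3, and c of failing both. Because B is nested in A,

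P(A passes and B fails) = P(Bin(20, a+b) ≥ 16) − P(Bin(20, a) ≥ 16).

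| Split a/b/c (%) | P(A passes) | P(B passes) | P(A passes, B fails) | Expected gap, 20 × b |
|---|---|---|---|---|
| 93/4/3 | 99.97% | 98.9% | 1.0% | 0.8 patients (4 points) |
| 86/4/10 | 95.7% | 86.3% | 9.4% | 0.8 patients (4 points) |
| 87/10/3 | 99.97% | 89.2% | 10.8% | 2 patients (10 points) |
| 77/20/3 | 99.97% | 49.9% | 50.1% | 4 patients (20 points) |

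The first row uses the literature split in Hypothesis and Objectives and takes every improved patient to be a 4-to-3 case. That split is retrospective and is not expressed in Tinnitus Handicap Inventory grades. The other three rows are assumed, to show the range.

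**Step 3: how the sponsor's series uses the word.** The baseline grades there were: "Nine patients presented with grade-4, 5 patients had grade-3, and 2 patients each had grade-2 and grade-1 tinnitus". That is 9 + 5 + 2 + 2 = 18 patients, of whom 5 + 2 + 2 = 9 were at grade 1 to 3 before stenting. Seventeen of the 18 are reported as resolved. The one who was not started at grade 1, so 9 − 1 = 8 of the 17 started at grades 1 to 3. For those 8, resolution must have meant something better than a grade they already had. The series does not name its scale, so the comparison assumes the same grades.

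**The case against.** The strongest case on the other side is that little turns on this in practice. The criteria agree in 11 of 12 cells. Both proportions will be reported and the case report form captures every grade, so neither result can be hidden. Only the Primary Outcome section contains a decision rule and it names 12 months; the other endpoint has no target and so cannot fail as written. The probabilities in Step 2 exist only because a bar was added to it, and no document supports a 20% rate of 4-to-3 moves.

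The sponsor's series even points the other way. Its only non-resolver was grade 1, so all nine grade-4 patients resolved and 0 of 9 went from 4 to 3. The 9 of 18 at grades 1 to 3 before stenting could not have entered this trial.

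Much of this stands. A reversed verdict is unlikely on the protocol's own figures, and the less favourable splits show a range, not a forecast. The 9 of 18 shows only how the word was used; it does not predict mislabelling in the trial. The 0 of 9 is reassuring but weak: it describes immediate resolution on an unnamed scale, and its one-sided 95% upper limit is 1 − 0.05^(1/9) = 28%.

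What the objection does not answer is that reporting both proportions does not say which is primary. The mislabelling needs no probability at all: the word moderate sits inside the definition of near-complete resolution.

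**Conclusion.** The concern holds. The protocol contradicts itself on its primary efficacy criterion, and its Primary Outcome section contradicts itself on what counts as resolution. Neither is a detail that a statistical analysis plan would ordinarily supply, because both conflicts are in the protocol's own text.

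The numerical effect is confined to patients who move from grade 4 to grade 3. On the literature split, with the 75% bar assumed for both criteria, the expected gap is 4 points and the chance of opposite verdicts is 1.0%. The documents give no reliable 4-to-3 rate at 12 months, so a larger gap cannot be excluded. The importance of the point rests on an open choice of headline result and on a misleading label, not on a likely change of conclusion.

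**What to change.** Reconcile the two sections before data are seen:

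- State one responder definition in identical words under Primary Outcome and Primary Endpoints, assessed at the 12-month visit that the Primary Outcome section already names, with its target proportion. If the change-from-baseline criterion is chosen, confirm explicitly that the more-than-75% target applies to it, since at present it has none.
- Make the other criterion, and the 1-, 6- and 24-month visits, secondary.
- Match the label to the threshold. If grade 3 is meant to count as success, replace the resolution wording with a description that covers moderate tinnitus. Otherwise, restrict the success grades to those that the wording supports.
- As a minor tidy-up, align the four severity words and three grade numbers with the 0 to 5 codes on the case report form. Grade 0 meets both criteria, so no patient's classification changes.

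The cost is wording in two sections and the grade labels. No patients, visits or data are added, because the form already records the grade at baseline and at all four visits. The one downside for the sponsor is that the reported success proportion may be lower if the stricter criterion is chosen.

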#### **Secondary Outcomes:**

- Long-term success of treatment (clinical recurrence rates over 24 months)
- Long-term patency of the stent (stent patency 12 months after treatment)
- Rate and severity of adverse events probably or possibly related to the treatment within a 24-month period

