**Reports on venous sinus stenting to treat pulsatile tinnitus in 100 patients (Table 1, attached document)**

Little has been published regarding endovascular treatment of pulsatile tinnitus due to venous stenosis in particular. We conducted a search of the literature available on PubMed detailing the outcomes of endovascular treatment of venous stenosis leading to pulsatile tinnitus and found that all were retrospective case reports or case series reports (Mathis et al. 1997, Donnet et al. 2008, Arac et al. 2009, Ahmed et al. 2011, Fields et al. 2013, Signorelli et al. 2011, Radvany et al. 2013, Baomin et al. 2014). From the search, 100 patients (Table 1) were found to have had endovascular treatment (stenting alone and stenting with angioplasty). Of those 100 patients, all but 3 patients reported resolved or improved tinnitus following the procedure. At follow-up of at least 2 months (ranging up to maximum 9 years), all treatments were considered successful with complete resolution of tinnitus except for 1 case which reported the return of tinnitus at a low level around 8 months (Mathis et al. 1997). All cases also reported long-term stent patency at follow-up. 8 patients experienced re-stenosis adjacent to the stent, 7 of which required re-stenting and 1 shunt placement. Only two cases experienced serious adverse events. One patient experienced vein perforation which eventually lead to a subdural hematoma. Another patient experienced subdural, subarachnoid and intracranial bleeding.

Baomin et al.'s (2014) paper was the most extensive report of endovascular treatment of pulsatile tinnitus due to venous stenosis. Forty-six cases were examined of patients who had failed medical treatment and masking therapies. Angioplasty and stenting were performed and all 46 patients reported immediate relief of tinnitus upon recovery from anesthesia. At 3-month follow-up, 2 patients reported recurrence of nonpulsatile tinnitus but this disappeared in both patients at the 6-month follow-up.

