**Follow-up (Patient Flow Chart, page 28)**

**Office visits**

Office visits with neurologic evaluation will be performed at one, six, twelve, and twenty-four months after treatment. At this time the patients will also fill the Tinnitus Handicap Inventory Questionnaire. The visits will last about 45 minutes.

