**Audiometric assessment**

Audiometric assessment will be performed at the three-month mark after stenting to assess inner ear function.

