#### Secondary Endpoints:

- No recurrence of tinnitus within 24 months after treatment
- Stent patency at 12 months after treatment
- Adverse events probably or possibly related to the treatment within a 24-month period after treatment

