### **Documenting Adverse Experiences:**

All adverse experiences are to be accurately recorded on the Adverse Events & Description of AE columns of the patient's CRF. Each experience will be categorized as either: serious AE, non-serious AE, or unexpected AE (see CRF). The date of onset as well as the duration of the experience will be recorded. In addition, the method used to treat the adverse experience and the outcome of the adverse experience will also be

noted. The investigator will attempt to assess the relationship of the experience (unrelated, remote, possible, probable, related) to the test procedure.

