**Patient Flow Chart**

**PRINT OUT OF ELECTRONIC CASE REPORT FORM**

Name: \_\_\_\_\_

Age: \_\_\_\_\_

DOB: \_\_\_\_\_

MRN: \_\_\_\_\_

Tinnitus Grade:  0  
 1  
 2  
 3  
 4  
 5Tinnitus Location:  Right  
 Left  
 BilateralVenous Dominance:  Right  
 Left  
 CodominantStenosis Location:  Right  
 Left  
 Bilateral

Stenting Date: \_\_\_\_\_

Stenting Result:  no residual stenosis  
 residual stenosis <50%  
 residual stenosis >50%  
 technical failure

Adverse Events:

- Serious
- Non-serious
- Unexpected

Description of Adverse Event

---

---

---

---

Tinnitus Grade:  0

Post-Stent (1 month)  1  
 2  
 3  
 4  
 5

Tinnitus Grade:  0

Post-Stent (6 mos)  1  
 2  
 3  
 4  
 5

Tinnitus Grade:  0

Post-Stent (12 mos)  1  
 2  
 3  
 4  
 5

Tinnitus Grade:  0

Post-Stent (24 mos)  1  
 2  
 3  
 4  
 5

MRV (12 mos)

- no residual stenosis or thrombosis
- in-stent stenosis <50%
- in-stent stenosis >50%
- new stenosis
- stent thrombosis

Any procedure-related adverse event after 24 months

---

---

---

---

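### Recurrence is an endpoint over a continuous 24 months, but tinnitus is graded at four visits, so a return that settles between visits has no planned record and, if short, is about half as likely to be caught after month 12

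*Protocol*

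**What the plan says.** Recurrence appears twice in the protocol. Under Secondary Outcomes it is "Long-term success of treatment (clinical recurrence rates over 24 months"). Under Secondary Endpoints it is "No recurrence of tinnitus within 24 months after treatment". Neither place defines a recurrence by grade, type of tinnitus or duration.

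The schedule is under Follow-up, Office visits: "Office visits with neurologic evaluation will be performed at one, six, twelve, and twenty-four months after treatment". The same paragraph adds: "At this time the patients will also fill the Tinnitus Handicap Inventory Questionnaire". One further contact is planned, but for another purpose: "Audiometric assessment will be performed at the three-month mark after stenting to assess inner ear function".

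The print-out of the electronic case report form has one tinnitus grade at baseline and one at each of the four visits, the last labelled "Post-Stent (24 mos". It has no field for a return since the previous visit, nor for when one began or ended. It does have a free-text adverse event field, and Documenting Adverse Experiences says: "All adverse experiences are to be accurately recorded on the Adverse Events & Description of AE columns of the patient's CRF".

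Data Analysis plans a simple proportion for each endpoint. Number of Patients gives 20.

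**The concern.** An endpoint about any recurrence in a 24-month window needs data that cover the window. Four readings of the current grade do not: tinnitus that comes back and settles between two visits leaves the same grades as tinnitus that never came back. Readings also thin out with time, with three visits in the first year and one in the second. The second year matters most for a claim of long-term success, which is how the Secondary Outcomes section describes this measure.

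The protocol's literature review gives some reason to ask. Of the 46 patients in its largest cited series it says: "At 3-month follow-up, 2 patients reported recurrence of nonpulsatile tinnitus but this disappeared in both patients at the 6-month follow-up". Under this trial's schedule, an episode confined to months 1 to 6 would fall between two gradings.

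A separate statistical analysis plan could not repair this. The gap is in data collection, and no analysis recovers an episode that nobody was asked about. With 20 patients, each one missed moves the reported proportion by 1/20 = 5 percentage points.

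**Working it through.** The protocol gives no detection figure for this endpoint, so there is nothing to reproduce. The check asks how likely a temporary return is to be present at the next planned grading.

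**Inputs from the protocol.** Visits at months 1, 6, 12 and 24 (Office visits) leave gaps of 6 − 1 = 5, 12 − 6 = 6 and 24 − 12 = 12 months.

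**Assumptions, not in the documents.** Onset is uniform in time. An episode has a fixed length d, varied below. A return present at a visit is recognised as a recurrence from the grade.

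**Formula.** In a gap of length L, an episode is present at the next visit with probability min(d, L)/L. Pooling gaps by length, months 1–12 give [min(d, 5) + min(d, 6)]/11 and months 12–24 give min(d, 12)/12.

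| d (months) | Caught, months 1–12 | Caught, months 12–24 | Ratio caught | Missed, months 1–12 | Missed, months 12–24 | Ratio missed |
|---|---|---|---|---|---|---|
| 1 | 2/11 = 0.18 | 1/12 = 0.08 | 0.46 | 0.82 | 0.92 | 1.12 |
| 3 | 6/11 = 0.55 | 3/12 = 0.25 | 0.46 | 0.45 | 0.75 | 1.65 |
| 5 | 10/11 = 0.91 | 5/12 = 0.42 | 0.46 | 0.09 | 0.58 | 6.4 |
| 6 | 11/11 = 1.00 | 6/12 = 0.50 | 0.50 | 0 | 0.50 | undefined |
| 8 | 1.00 | 8/12 = 0.67 | 0.67 | 0 | 0.33 | undefined |
| 12 | 1.00 | 1.00 | 1.00 | 0 | 0 | undefined |

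For d up to 5 months the ratio caught is constant: (d/12)/(2d/11) = 11/24 = 0.46. Against the 6-to-12-month gap alone it is 6/12 = 0.50. Over the whole of months 1–24, a 3-month episode is caught with probability (3 + 3 + 3)/23 = 0.39 and missed with probability 14/23 = 0.61.

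**Sensitivity.** If lengths vary exponentially with mean m, the probability missed in a gap is 1 − (m/L)(1 − exp(−L/m)).

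- m = 1: missed 0.819 and 0.917, so caught 0.181 and 0.083, ratio 0.46.
- m = 3: missed 0.543 and 0.755, so caught 0.457 and 0.245, ratio 0.54.
- m = 5: missed 0.395 and 0.621, so caught 0.605 and 0.379, ratio 0.63.

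So about half is right for short episodes and weakens as they lengthen.

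**Scale in 20 patients, for illustration.** Applying the cited 2 in 46 gives 20 × 2/46 = 0.87 patients with a temporary return. If each lasted 3 months, 0.87 × 0.61 = 0.53 would be missed, about half a patient or 2.6 percentage points. Those two cases were nonpulsatile, so this only indicates an order of size.

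**The case against.** The strongest reply is that the protocol documents no pulsatile tinnitus that returned and then settled. The two temporary cases were nonpulsatile, a type that the background section attributes to a different source and that the exclusion criteria rule out at entry. The one pulsatile-series return in the follow-up summary, low-level at around 8 months, is not described as temporary, and the institution's own 18 patients with pulsatile tinnitus had none. If recurrence follows re-narrowing of the sinus, it may well persist and be graded at the next visit. This stands, and it makes the bias conditional. It does not remove the gap, because the endpoint speaks of tinnitus without restricting the type, and nothing rules out a short pulsatile return.

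It is also fair to say that the protocol never states that recurrence is judged from the grade alone. A clinician could ask about it at the visit, an adverse experience is recorded with onset and duration, and a return needing inpatient care would count as serious. Some episodes could be caught this way. But no instruction sends a return of tinnitus down that route, and the form provides no place for the answer. The Patient Flow Chart could not be read in the copy reviewed.

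A reader might infer that returns are missed twice as often after month 12. The figures do not support that: the ratio of misses is 1.12 at 1 month, 1.65 at 3 months and 6.4 at 5 months, and only detection is roughly halved. A reader might also infer that recurrence will appear to fall in year 2. That would need a comparison by year, and Data Analysis plans one proportion per endpoint.

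**Conclusion.** The mismatch between a continuous 24-month endpoint and four point-in-time grades is real, and it lies in the data to be collected. A return that starts and settles between visits has no planned record. Under uniform onset, one lasting up to about 5 months is 0.46 times as likely to be caught in year 2 as in months 1–12. A recurrence that persists to the next visit is seen in either year, with its onset known only to within the gap.

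That the recurrence proportion is biased low cannot be stated as fact. It would be biased low if short episodes occur, by an amount that depends on frequency and duration, neither of which the documents give for pulsatile recurrence. This is a secondary endpoint in a descriptive single-arm study of 20 patients. The point deserves action because the change is cheap and must be made before the data are collected.

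**What to change.** At the existing 6-, 12- and 24-month visits, add one fixed item to the case report form: *Has the tinnitus returned at any time since the last visit? Pulsatile or not; date started; date stopped or ongoing.* State in the Secondary Outcomes and Secondary Endpoints sections that a recurrence is counted if either this item or the visit grade shows one.

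If the sponsor prefers not to add the item, rename the endpoint *tinnitus recurrence present at the 6-, 12- or 24-month visit*, so that the claim matches the data.

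The first option costs one form item and one sentence in each of two sections, with no new visit. Its drawbacks are recall error over up to 12 months and a possibly less favourable recurrence figure. The second costs only a change of wording, but gives up the claim about the whole period.
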